### **Study populations:**

The SAD, MAD and CSF capture study populations will be made up of healthy male and female adult volunteers (aged 18-65 years) who meet all defined inclusion/exclusion criteria.

Procedure	Screening (Day	]				
	-28 to Day -2)	Day -1	Day 1	Day 2	Day 3	Day 5-8
Informed Consent	X					
Eligibility Criteria	X	X				
Demographics	X					
Height	X					
Weight, BMI	X	X			X	
Medical history	X	X			X	X
Physical Examination*	X	X		X	X	
Vital Signs**	X	X	X	X	X	
ECG**	X	X	X	X	X	
Urine Drug Test	X	X				
Urine Cotinine	X	X				
Alcohol Breath Test	X	X				
Pregnancy Test (Females)^	X	X				
Serology (Hepatitis B.	X					
Hepatitis C, HIV)						
Clinical Lab. Tests (Hema	X	X	X	X		
Chem., Urinalysis)						
Prior and Concom. Meds.	X	X		X	X	X
Ocular Examinations***		X			X	
Modified Observer's			X			
Assess. of Alert./Sed.						
(MOAA/S)****						
Suicide Screen (C-SSRS)	X	X	X	X		
Mood and Cognitive		X	X	X		X
Assessment (POMS)						
Clin. Admin. Diss. States		Х	X			
Scale (CADSS)*****						
IV Drug Administration			X			
Blood Sample Collection			X	X	X	
(PK)						
Urine Sample Collection			X	X		
(PK)						
qEEG			X			
Confinement			X			
Adverse Events			X	Χ	X	X
Outpatient Visit					Х	
Phone Call						X

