## Methodology/study design:

A 6-cohort single ascending dose (SAD) study will be conducted in healthy volunteers utilizing a slow-infusion intravenous (IV) route of administration. Standard safety, pharmacokinetics (PK) and qEEG monitoring will be evaluated at all dose levels. Subsequently, a 2-cohort multiple ascending dose (MAD) study will be conducted. Doses will be administered on days 1,4, 8, and 11. Standard safety parameters will be monitored, and PK will be evaluated at all dose levels.

Finally, a single cohort of healthy volunteers will receive a single dose by slow-infusion IV and have PK samples collected from both blood and cerebrospinal fluid (CSF).

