## Safety:

Safety will be assessed throughout the study. Baseline and follow-up safety assessments will include height, body mass index (BMI), weight, temperature, medical, visual and ocular history, physical examinations, ocular examinations, visual acuity, color vision tests, electrocardiograms (ECGs), vital signs (VS), clinical laboratory tests (hematology, serum chemistry, and urinalysis), the Profile of Mood States (POMS), the Columbia-Suicide Severity Rating Scale (C-SSRS), the Clinician Administered Dissociative States Scale (CADSS), and adverse events (AEs). Safety assessments will include AEs, ECGs, VS, clinical laboratory results, and physical observations. Assessment of each Subject's level of alertness/Sedation will be accomplished using the Modified Observer's Assessment of Alertness/Sedation (MOAA/S).

Evaluation of safety in the MAD study will utilize the same safety assessments used in the SAD study.

Evaluation of safety in the CSF capture study will utilize the same safety assessments used in the SAD and MAD study with the exception of the CADSS and MOAA/S assessments.

Monitoring of AEs will be governed by change from baselines established during prescreening and Day -1 examinations and clinical laboratory tests. AEs will be coded using the Medical Dictionary for Regulatory Activities (MedDRA) and summarized by system organ class and preferred term, by severity, by relationship to study drug and study procedure, and by study drug dose.

Dose escalation in the SAD study or continued dosing in the MAD study may be stopped according to the predefined halting rules or if a Subject's scores demonstrate acute suicidality on the C-SSRS assessment or at the discretion of the study Principal Investigator and/or sponsor.

Determination of whether to escalate to the next dose level in the SAD study or continue dosing in the MAD will be made by the Principal Investigator in consultation with the Medical Monitor and Study Sponsor.

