#### Table 1: SAD schedule of assessments and procedures

An early termination visit will be scheduled on an ad hoc basis for any subject who withdraws from the study. \* Physical examinations can be conducted at any additional time at the judgement of the Principal Investigator (eg, to evaluate an adverse event)

^FSH for postmenopausal women at screening visit

\*\* Day 1 Timepoints: 1-hr preinfusion, and 1, 2, 4, 8, and 12 hr after the start of the infusion.

\*\*\* Ocular examinations include visual acuity and color vision tests.

\*\*\*\* On Day 1, MOAA/S is performed preinfusion, during the infusion at approximately 20 min after start of infusion, 40 min after start of infusion, and approximately 1 hr after the start of the infusion.

\*\*\*\*\* On Day 1, CADSS is performed preinfusion and approximately 40 min and 80 min after the start of the infusion.

Procedure	Screening					Confin	ement					Follo	ow-Up
	(Day -28 to Day -2)	Day -1	Day 1	Day 2	Day 4	Day 5	Day 7	Day 8	Day 9	Day 11	Day 12	Day 15	Day 17-19
Informed Consent	X												
Eligibility Criteria	X	X											
Demographics	X												
Height	X												
Weight, BMI	X	X									Х		
Medical history	X	X									Χ	X	X
Physical Examination*	X	X					Χ				Χ		
Vital Signs**	X	X	Х		X	X	X	X	X	X	X		
ECG**	X	X	Х		X	X	X	X	X	X	X		
Urine Drug Test	X	X					X						
Alcohol Breath Test	X	X					X						
Pregnancy Test	X	X					X						
(Females)^													
Serology (Hepatitis C,	X												
Hepatitis B, HIV)													
Clinical Lab. Tests	Х		Х	Х				Х	Х	Х	Х		
(Hema., Chem.,													
Urinalysis)													
Prior and Concom. Meds.	X	X	X			X	X				X	X	X
Ocular Examinations***		X		X						X	X		
Modified Observer's			Х		Х			Х		Х			
Assess. of Alert./Sed.													
(MOAA/S)****													
Suicide Screening (C- SSRS)	X	X	X	X	X	X	X	X	X	X	X	X	X
Mood and Cognitive		X	X	X	X	X	X	X	X	X	X	X	X
Assessment (POMS)													
Clin. Admin. Diss. States			X		X			X		X			
Scale (CADSS)*****													
IV Drug Administration			X		X			X		X			
Blood Sample Coll. (PK)			X	X	X			X		X	X		
Check-in & Confinement		X	X	X	X		X	X	X	X			
Check-out*****						X					X		
Adverse Events			X	X	X	X		X	X	X	X	X	X
Outpatient Visit													
Phone Call												X	Х

Table 2: MAD schedule of assessments and procedures

An early termination visit will be scheduled on an ad hoc basis for any subject who withdraws from the study.

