#### Figure 1: Visual representation of timeline of key events in the SAD dosing period.

- A Pharmacokinetics and clin. lab blood draw (PK): Pre-infusion, approximately 24 and 48 hrs after start of infusion
- ▲ Pharmacokinetics blood draw (PK): End-of-infusion (40 min), 1, 2, 4, 8, 12 hrs after start of the infusion
- ◆ Pharmacokinetics urine capture (PK): Up to 3 per Subject; collected 0-4, >4-8, >8-12, >12-24 hrs after the start of infusion
- \* Vitals/Electrocardiograms (ECG): Approximately 1 hr pre-infusion and 1, 2, 4, 8 and 12 hrs after the start of infusion
- Profile of mood states (POMS): Day -1, within approximately 4 and 24 hrs after the start of infusion
- Columbia-suicide severity rating scale (C-SSRS): Day -1, within approximately 4 and 24 hrs after the start of infusion
- Modified observer's assessment of alertness/sedation (MOAA/S): Pre-infusion, and approximately 20 min, 40 min and 1 hr after start of infusion
- Clinician administered dissociative states scale (CADSS): Day -1, Pre-infusion, approximately 40 min and 80 min after start of infusion
- —★ Resting-State EEG and visual evoked potentials (checkerboard): 5 min resting state followed by 5 min visual evoked
  potential paradigm beginning approximately 40 min pre-infusion, and 40 min and 160 min after the start of infusion

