#### Table 6: CSF Capture study planned dosing levels

## 8.0 STUDY DESIGN RATIONALE

## 8.1 STUDY DRUG

The antidepressant activity of racemic ketamine and the recent approval of S-(+)ketamine (esketamine, SpravatoTM) have proven to be major advances for individuals with TRD. However, several issues surround these drugs including unwanted side effects and the potential for abuse. Further, inconsistencies surround the purported mechanism of action (NMDAR antagonism) as other investigational drugs with optimized potency for this target lack consistent antidepressant activity. There are also PD questions given that ketamine is eliminated on a timescale (hours) that is inconsistent with the effect duration (days). (2R,6R)-Hydroxynorketamine is a metabolite following ketamine administration. (2R,6R)-Hydroxynorketamine possesses strong antidepressant activity in multiple models of depression and anxiety. (2R,6R)-Hydroxynorketamine is a weak NMDAR antagonist and, therefore, is devoid of unwanted side-effects including sedation, dissociation and addictive potential as tested in animal models. (2R,6R)-Hydroxynorketamine is manufactured as the HCl salt which yields a single polymorph and crystal form and is stable as both a solid and as a solution in multiple formulants. The investigational drug product (IDP) is a solution-based formulation of (2R,6R)-Hydroxynorketamine in 25 mM phosphate buffer.

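### In the SAD and CSF parts the structured suicidality screen stops about 24 h after dosing, although two later contacts already take place and the MAD part screens at every contact

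*Protocol*

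**What the plan says.** **Single-dose parts.** Protocol Table 1 (SAD) and Table 3 (CSF) mark the row "Suicide Screen (C-SSRS" at screening, Day -1, Day 1 and Day 2, and leave Day 3 and Day 5-8 blank. SAP 3.1 and 3.3 show the same pattern. The legends to Figures 1 and 7 agree: "Columbia-suicide severity rating scale (C-SSRS): Day -1, within approximately 4 and 24 hrs after the start of infusion". In the same tables the row "Adverse Events" is marked through Day 5-8, medical history is marked at Day 3 and Day 5-8, and the POMS (row "Mood and Cognitive") is repeated at Day 5-8. The Synopsis ends the residential stay on Day 2.

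**MAD part.** Table 2 marks "Suicide Screening (C- SSRS" in every column, through the Day 15 and Day 17-19 phone calls. The Synopsis says: "Evaluation of safety in the MAD study will utilize the same safety assessments used in the SAD study".

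**Use of the instrument.** The Synopsis (Safety) and protocol section 8.7 let escalation be stopped if C-SSRS scores show acute suicidality. Section 10.3 bases the SAD escalation review on available safety data to Day 3. SAP 9.1 lists the C-SSRS among the primary endpoints, and SAP 12.12 says no descriptive statistics will be given for it.

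**The concern.** The C-SSRS is the only instrument in the study that asks directly about suicidal ideation and behaviour. In the single-dose parts it stops at about the time the subject leaves the unit, while other safety questions continue for several days. The documents give no reason for stopping it there, and in the MAD part it continues by phone to the last contact.

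Two things are at stake. First, after discharge suicidality could come to light only through general adverse-event or history questioning, which does not ask about it in a structured way. This includes subjects at 4.0 mg/kg, a level planned only in the SAD part (Table 4; the MAD levels in Table 5 are 1.0 and 2.0 mg/kg). Second, the SAD escalation review runs to Day 3 and C-SSRS findings may stop escalation, but the Day 3 visit adds no C-SSRS result to that review.

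**Working it through.** The plan states no figure to reproduce. The check is a reading of the schedules and a count of days.

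**Inputs**
- SAD and CSF: dose on Day 1; last C-SSRS on Day 2; later contacts at Day 3 and Day 5-8 (Tables 1 and 3; Synopsis, duration of participation).
- MAD: "Doses will be administered on days 1,4, 8, and 11", so the last dose is on Day 11; C-SSRS at Day 15 and Day 17-19 (Table 2).
- Planned subjects: SAD 48 and MAD 16 (Synopsis). The CSF cohort is 6 in the Synopsis but 8 in protocol sections 7.0 and 12.4 and in SAP section 10, so both are carried.

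**Schedules side by side**

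| | SAD and CSF | MAD |
|---|---|---|
| Schedule columns with C-SSRS | 4 of 6 | 13 of 13 |
| Contacts after the residential stay | Day 3, Day 5-8 | Day 15, Day 17-19 |
| C-SSRS at those contacts | neither | both |
| AEs and medical history at those contacts | both | both |

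**Days from last dose (visit day minus last dosing day)**
- Last C-SSRS, SAD and CSF: 2 − 1 = 1 day.
- Last contact, SAD and CSF: 5 − 1 = 4 to 8 − 1 = 7 days.
- Follow-up after the last C-SSRS: 4 − 1 = 3 to 7 − 1 = 6 days.
- MAD C-SSRS after the last dose: 15 − 11 = 4 days, then 17 − 11 = 6 to 19 − 11 = 8 days, which is the last contact.
- SAD escalation review: data to Day 3, 3 − 1 = 2 days after dosing, with C-SSRS to day 1 of those 2.

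**Subjects on the short schedule**
- CSF of 6: (48 + 6)/(48 + 16 + 6) = 54/70 = 77.1%.
- CSF of 8: (48 + 8)/(48 + 16 + 8) = 56/72 = 77.8%.

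**Could another instrument stand in?** The POMS form in the protocol's Appendix 2 has mood items such as hopelessness and worthlessness, but none on suicidal thoughts or acts. It is not marked at Day 3 in Tables 1 and 3.

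**Could this be a misread table?** That is unlikely. The protocol tables, the SAP tables and the two figure legends all end the C-SSRS at the same point.

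**The case against.** The strongest reply is that this is a consistent design choice. Every schedule agrees, and the Synopsis sentence on using the same assessments in MAD as in SAD can fairly be read as naming the instruments and not their timing. The stopping ground is acute suicidality, which assessments at about 4 h and 24 h address, and the itemised halting rules in section 10.3 contain no C-SSRS criterion. Volunteers are healthy, and a history of mental illness or suicidal ideation excludes them (section 9.3), so few events are to be expected. Adverse-event monitoring runs to the end of the study. All of this stands. It lowers the priority of the change, but it does not explain why the screen is dropped from contacts that take place anyway.

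Three stronger readings are tempting, and the documents do not support them.

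- *The unequal schedules would bias a comparison of SAD with MAD.* No such comparison is planned. SAP section 7 reports the parts separately without hypothesis tests, and SAP 12.12 plans no C-SSRS summary. The primary-endpoint label in SAP 9.1 does not change that.
- *The protocol says effects of this drug family outlast exposure by days.* Section 8.1 says only that "ketamine is eliminated on a timescale (hours) that is inconsistent with the effect duration (days". It speaks of ketamine, while discussing its antidepressant action and mechanism. It does not apply the statement to the study drug or mention delayed suicidality.
- *Suicidality after Day 2 would go unasked and unseen.* Adverse events and medical history are taken at both later contacts and the POMS at the second. What is missing is the structured question.

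Protocol section 8.5 also says the MAD and CSF doses were accepted on SAD outcomes, which suggests that SAD dosing may be finished. If so, editing Table 1 cannot help the 48 planned SAD subjects.

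**Conclusion.** The point holds as a gap in structured safety ascertainment, and as a cheap improvement. C-SSRS coverage after a single dose is about 1 day of a 4-to-7-day follow-up, which leaves 3 to 6 days and two existing contacts without it, on a schedule that applies to about 77% of planned subjects. The SAD escalation review contains no C-SSRS later than Day 2.

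These figures describe coverage and not risk. The documents give no event rate from which a number of missed cases could be estimated, and they do not name delayed suicidality as an expected risk of this drug. The conclusion assumes that the blank cells are intended, as their agreement across the tables and legends indicates. How many subjects can still benefit depends on whether SAD dosing is complete. At the least, the CSF cohort (6 or 8 subjects) and any added SAD cohort could.

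**What to change.** 1. Reconcile the single-dose schedules with MAD by marking the C-SSRS at the Day 3 visit and the Day 5-8 call in protocol Tables 1 and 3 and SAP 3.1 and 3.3, for the CSF cohort and any SAD cohort still to be dosed. That is four protocol cells and four SAP cells. If the Figure 1 and Figure 7 legends are meant to be complete, align them too; they already omit the Day 5-8 POMS.
2. State which form version and recall period apply after dosing. Both documents append only the baseline/screening form, which asks about lifetime and past months or years, and neither says what recall period the MAD follow-up calls use.
3. For subjects already dosed, state in the SAP that C-SSRS coverage after a single dose is about 24 h, so that an absence of findings is not read as covering the whole follow-up.
4. If the shorter window is deliberate, give the reason in the protocol.

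The cost is a few minutes at two contacts that already take place, the second by phone as in MAD. No visit is added, and no dosing or halting rule changes.

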#### Table 1: SAD schedule of assessments and procedures

An early termination visit will be scheduled on an ad hoc basis for any subject who withdraws from the study. \* Physical examinations can be conducted at any additional time at the judgement of the Principal Investigator (eg, to evaluate an adverse event)

^FSH for postmenopausal women at screening visit

\*\* Day 1 Timepoints: 1-hr preinfusion, and 1, 2, 4, 8, and 12 hr after the start of the infusion.

\*\*\* Ocular examinations include visual acuity and color vision tests.

\*\*\*\* On Day 1, MOAA/S is performed preinfusion, during the infusion at approximately 20 min after start of infusion, 40 min after start of infusion, and approximately 1 hr after the start of the infusion.

\*\*\*\*\* On Day 1, CADSS is performed preinfusion and approximately 40 min and 80 min after the start of the infusion.

Procedure	Screening					Confin	ement					Follo	ow-Up
	(Day -28 to Day -2)	Day -1	Day 1	Day 2	Day 4	Day 5	Day 7	Day 8	Day 9	Day 11	Day 12	Day 15	Day 17-19
Informed Consent	X												
Eligibility Criteria	X	X											
Demographics	X												
Height	X												
Weight, BMI	X	X									Х		
Medical history	X	X									Χ	X	X
Physical Examination*	X	X					Χ				Χ		
Vital Signs**	X	X	Х		X	X	X	X	X	X	X		
ECG**	X	X	Х		X	X	X	X	X	X	X		
Urine Drug Test	X	X					X						
Alcohol Breath Test	X	X					X						
Pregnancy Test	X	X					X						
(Females)^													
Serology (Hepatitis C,	X												
Hepatitis B, HIV)													
Clinical Lab. Tests	Х		Х	Х				Х	Х	Х	Х		
(Hema., Chem.,													
Urinalysis)													
Prior and Concom. Meds.	X	X	X			X	X				X	X	X
Ocular Examinations***		X		X						X	X		
Modified Observer's			Х		Х			Х		Х			
Assess. of Alert./Sed.													
(MOAA/S)****													
Suicide Screening (C- SSRS)	X	X	X	X	X	X	X	X	X	X	X	X	X
Mood and Cognitive		X	X	X	X	X	X	X	X	X	X	X	X
Assessment (POMS)													
Clin. Admin. Diss. States			X		X			X		X			
Scale (CADSS)*****													
IV Drug Administration			X		X			X		X			
Blood Sample Coll. (PK)			X	X	X			X		X	X		
Check-in & Confinement		X	X	X	X		X	X	X	X			
Check-out*****						X					X		
Adverse Events			X	X	X	X		X	X	X	X	X	X
Outpatient Visit													
Phone Call												X	Х

Table 2: MAD schedule of assessments and procedures

An early termination visit will be scheduled on an ad hoc basis for any subject who withdraws from the study.

\* Physical examinations can be conducted at any additional time at the judgement of the Principal Investigator (eg, to evaluate an adverse event)

^FSH for postmenopausal women at screening

\*\* Dosing Day timepoints: 1-hr preinfusion, and 1, 2, 4, 8, and 12 hr after the start of the infusion.

\*\*\* Ocular examinations include visual acuity and color vision tests.

\*\*\*\* On Dosing days MOAA/S is performed preinfusion, during the infusion at approximately 20min after start of infusion, 40 min after start of infusion, and approximately 1 hr after the start of the infusion. \*\*\*\*\* On Dosing days, CADSS is performed preinfusion and approximately 40 min and 80 min after the start of the infusion.

\*\*\*\*\*\* See Figure 2 for details regarding check-in/check-out schedule

Procedure	Screening (Day					
	–28 to Day -2)	Day -1	Day 1	Day 2	Day 3	Day 5-8
Informed Consent	X					
Eligibility Criteria	X	Х				
Demographics	X					
Height	X					
Weight, BMI	X	X			X	
Medical history	X	X			X	X
Physical Examination*	X	Х		X	X	
Vital Signs**	X	Х	X	X	X	
ECG**	X	Х	X	X	X	
Urine Drug Test	X	Х				
Urine Cotinine	X	Х				
Alcohol Breath Test	X	Х				
Pregnancy Test (Females)^	X	Х				
Serology (Hepatitis B,	X					
Hepatitis C, HIV)						
Clinical Lab. Tests (Hema.,	X	Х	X	X		
Chem., Urinalysis)						
Prior and Concom. Meds.	X	X		X	X	X
Ocular Examinations***		X			X	
Suicide Screen (C-SSRS)	X	X	X	X		
Mood and Cognitive		Х	X	X		X
Assessment (POMS)						
IV Drug Administration			X			
Blood Sample Collection			X	X		
(PK)						
Cerebrospinal Fluid			X			
Collection (PK)						
Confinement			X			
Adverse Events			X	X	X	X
Outpatient Visit					X	
Phone Call						X

### Table 3: CSF Capture Study schedule of assessments and procedures

An early termination visit will be scheduled on an ad hoc basis for any subject who withdraws from the study. \* Physical examinations can be conducted at any additional time at the judgement of the Principal Investigator (eg, to evaluate an adverse event)

^FSH for postmenopausal women at screening visit

\*\* Day 1 Timepoints: 1-hr preinfusion, and 1, 2, 4, 8, and 12 hr after the start of the infusion.

\*\*\* Ocular examinations include visual acuity and color vision tests.

#### Figure 1: Visual representation of timeline of key events in the SAD dosing period.

- A Pharmacokinetics and clin. lab blood draw (PK): Pre-infusion, approximately 24 and 48 hrs after start of infusion
- ▲ Pharmacokinetics blood draw (PK): End-of-infusion (40 min), 1, 2, 4, 8, 12 hrs after start of the infusion
- ◆ Pharmacokinetics urine capture (PK): Up to 3 per Subject; collected 0-4, >4-8, >8-12, >12-24 hrs after the start of infusion
- \* Vitals/Electrocardiograms (ECG): Approximately 1 hr pre-infusion and 1, 2, 4, 8 and 12 hrs after the start of infusion
- Profile of mood states (POMS): Day -1, within approximately 4 and 24 hrs after the start of infusion
- Columbia-suicide severity rating scale (C-SSRS): Day -1, within approximately 4 and 24 hrs after the start of infusion
- Modified observer's assessment of alertness/sedation (MOAA/S): Pre-infusion, and approximately 20 min, 40 min and 1 hr after start of infusion
- Clinician administered dissociative states scale (CADSS): Day -1, Pre-infusion, approximately 40 min and 80 min after start of infusion
- —★ Resting-State EEG and visual evoked potentials (checkerboard): 5 min resting state followed by 5 min visual evoked
  potential paradigm beginning approximately 40 min pre-infusion, and 40 min and 160 min after the start of infusion

## Figure 2: Visual representation of timeline of key events in the MAD study.

#### Figure 3: Visual representation of timeline of key events for Dose #1 in the MAD study.

#### Dose #1 (Tuesday)

- A Pharmacokinetics and clin. lab blood draw
- Pharmacokinetics blood draw only
- \* Vitals/Electrocardiograms (ECG): Approximately 1 hr pre-infusion and 1, 2, 4, 8 and 12 hrs after the start of infusion
- Profile of mood states (POMS): Day -1, within approximately 4 and 24 hrs after the start of infusion
- Columbia-suicide severity rating scale (C-SSRS): Day -1, within approximately 4 and 24 hrs after the start of infusion
- Modified observer's assessment of alertness/sedation (MOAA/S): Pre-infusion, and approximately 20 min, 40 min and 1 hr after start of infusion
- Clinician administered dissociative states scale (CADSS): Day -1, Pre-infusion, approximately 40 min and 80 min after start of infusion

#### Figure 4: Visual representation of timeline of key events for Dose #2 in the MAD study.

Dose #2 (Friday)

- ▲ Pharmacokinetics blood draw only
- \* Vitals/Electrocardiograms (ECG): Approximately 1 hr pre-infusion and 1, 2, 4, 8 and 12 hrs after the start of infusion
- Profile of mood states (POMS): Day -1, within approximately 4 and 24 hrs after the start of infusion
- Columbia-suicide severity rating scale (C-SSRS): Day -1, within approximately 4 and 24 hrs after the start of infusion
- Modified observer's assessment of alertness/sedation (MOAA/S): Pre-infusion, and approximately 20 min, 40 min and 1 hr after start of infusion
- Clinician administered dissociative states scale (CADSS): Day -1, Pre-infusion, approximately 40 min and 80 min after start of infusion

